2.0 STUDY DESIGN

Primary Hypothesis:

Due to its different but relevant mechanism of action, guanfacine will be an effective adjunct to lidocaine in trigeminal nerve block for the treatment of painful trigeminal neuropathy by enhancing and prolonging pain relief compared to lidocaine alone.

Endpoints

The following endpoints will be measured to evaluate the exploratory objectives of the study assessing guanfacine and lidocaine in combination compared to lidocaine alone, in pain management in the painful trigeminal neuropathy patient.

- Primary endpoint: time to return to baseline pain (VAS) measurement after treatment with guanfacine as adjuvant to 1% lidocaine compared to 1% lidocaine alone
- Safety endpoint: comparable side effect profile of combination product compared to lidocaine alone on relevant adverse event measures: sedation, local site reaction, confusion
- Secondary endpoint: pain intensity after treatment to be measured throughout the follow-up periods on a visual analog scale (VAS)
- Secondary endpoint: quality of life after treatment to be measured using PROMIS Global Health -10 SF during the follow-up periods
- Secondary endpoint: frequency of acute trigeminal nerve pain attacks during the follow-up periods
- Secondary endpoint: total amount of rescue medications (opioid and non-opioid analgesics) for pain management during the follow-up periods
- Secondary endpoint: time to first rescue medication during the follow-up periods

Experimental Design

The trial is designed as a single-center, randomized, double-blind, controlle, 2x2 crossover pilot study with two arms: study drug (guanfacine and lidocaine combination) and active control (lidocaine alone). The target sample size is 30 study drug vs. 30 active control.

Not all participants that are randomized and initiate the first arm of the trial will *necessarily* complete *both* arms of the crossover trial. Based on previous experience, initiating the first arm of the cross over trial in 40 participants should be sufficient reach the full sample size (30 study drug vs. 30 active control). The trial will be complete and enrollment will cease upon reaching the full proposed sample size (30 study drug vs. 30 active control).

Approximately 80 patients meeting preliminary enrollment criteria will be consented for screening with the goal of roughly half being eligible to randomize and begin participation in the trial.

Inclusion Criteria

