If VAS < 5 on the pain scale, participants will not be eligible for second trigeminal nerve block during the visit. Study nurse will continue monitoring the participant's pain intensity (daily through day 15, and weekly thereafter) to see if the participant pain is above 5 on the pain scale and eligible for the second block. In general, the study intends that participants would receive both treatments unless they experience intolerable toxicity. If a participant is unable or ineligible to receive second trigeminal nerve block, then the participant's data collected during the first nerve block will be included in the analysis. In addition, a replacement participant will be enrolled so that the minimum number of 30 for each arm is reached. An intention-to-treat analysis will be done post-hoc to evaluate any differential progress to second block between the initial randomized groups.

Second trigeminal nerve block procedure: Participant will receive second trigeminal nerve block followed by monitoring for pain intensity at 30-minute time intervals for the first 8 hours after block, again allowing responses all the way until the next time point.

Second follow-up period (14 days)

Participants will be monitored once daily at the same timepoint for 14 days using text message generated using the Twilio application or recorded on a paper diary. Participants will also be monitored for any use of rescue medication (analgesics) once daily. The study nurse will monitor participants once weekly for overall quality of life via phone call. Participants will be instructed to contact the study nurse with any adverse events directly by phone.

[figure not shown]

Figure: 1. Study Schema

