minutes. The sample size for the proposed study was selected to achieve at least 80% power to detect a 20% or greater increase in the duration of pain relief after treatment with lidocaine plus guanfacine as an adjuvant (treatment group). This corresponds to a mean difference of 28 minutes. Again, although this degree of difference is not likely to be clinically meaningful, we are conducting this trial as a proof of mechanism only. If successful, we would pursue a modified formulation of guanfacine such that delivery was extended and pain relief duration was considerably longer. A simulationbased power analysis was implemented using linear mixed-effects regression as described above. Both betweenand within-subjects variability conservatively assumed to have standard deviation 30

minutes. Under these conditions, 30 participants will ensure approximately 90% power to detect a significant mean difference (28 minutes or greater in pain relief duration). **Figure 2** illustrates the estimated statistical power for somewhat larger and smaller effect sizes (i.e., 15%, 20%, and 25% increase in pain relief duration), for a variety of sample sizes.

Dropout and intent-to-treat: If VAS < 5 on the pain scale, participants will not be eligible for second trigeminal nerve block during the visit. Study nurse will continue monitoring the participant's pain intensity daily (days 15-28) to monitor when the participant pain is above 5 on the pain scale and eligible for the second block. In general, the study intends that participants would receive both treatments unless they experience intolerable toxicity. If a participant is unable or ineligible to receive second trigeminal nerve block, then the participant's data collected during the first nerve block will be included in the final analysis. In addition, a replacement participant will be enrolled so that the minimum number of 30 for each arm is reached. An exploratory analysis will be done post-hoc to evaluate any differential progress to second block between the initial randomized groups. Approximately 70 people with painful trigeminal neuropathy will be evaluated at Vanderbilt University Medical Center to determine if they are eligible to take part in this study. We expect to consent 70 subjects with 30 completing the full study.

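### Do the differing consent forecasts (about 80 and 70), and the unwritten unit of the target of 30 per arm, call for a change to the plan?

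*Combined protocol and SAP*

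**What the plan says.** Section 2.0 (Experimental Design) gives one recruitment flow: "Approximately 80 patients meeting preliminary enrollment criteria will be consented for screening with the goal of roughly half being eligible to randomize". It acknowledges that some who start will not complete both arms, and adds that "initiating the first arm of the cross over trial in 40 participants should be sufficient reach the full sample size", that size being 30 study drug and 30 active control. It then sets the end of recruitment: "enrollment will cease upon reaching the full proposed sample size (30 study drug vs. 30 active control").

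Section 9.1 (Dropout and intent-to-treat) gives another: "Approximately 70 people with painful trigeminal neuropathy will be evaluated at Vanderbilt University Medical Center to determine if they are eligible", and "We expect to consent 70 subjects with 30 completing the full study". It states neither an eligibility rate nor a number of starters.

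On one-block participants, Section 5.0 provides for the case: "If a participant is unable or ineligible to receive second trigeminal nerve block", the first-block data stay in the analysis, and "a replacement participant will be enrolled so that the minimum number of 30 for each arm is reached". Section 9.1 repeats this rule. For power, Section 9.1 says "30 participants will ensure approximately 90% power to detect a significant mean difference", for a difference of 28 minutes.

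**The concern.** Two sections give different numbers for people consented to the same single-center trial, and neither is superseded text. At the Section 2.0 eligibility rate of one half, 70 consents would give 35 starters, not 40.

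The second part matters more. The rule that ends enrollment is expressed per arm, and in a crossover 30 versus 30 can mean 30 people with both blocks or 60 blocks split evenly. Because first-block data from non-completers are kept, a reader could suppose that those blocks fill the arms. Enrollment could then stop with fewer than 30 completers, and the power stated for 30 participants would not apply. At stake would be the point at which recruitment ends and whether the stated 90% describes the trial that is run.

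**Working it through.** **Inputs.** Section 2.0: 80 consented, about half eligible, 40 starters, target 30 versus 30. Section 9.1: 70 consented, 30 completers; 28-minute difference; between- and within-subject SD both 30 minutes. Section 9.0: 5% type-I error, two-degree-of-freedom test of treatment and treatment-by-order, random intercept per participant. Assumed for the power figures: no period effect, equal numbers per order, and missing second blocks unrelated to outcome.

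**1. The plan's own power.** With 30 participants, all with both blocks, noncentrality = 30 × 28² / (2 × 30²) = 13.07. Two-degree-of-freedom chi-square power at 5% is 90.9%; a simulated likelihood-ratio test (600 runs) gave 90.3%. The stated figure of about 90% reproduces with 30 two-block participants.

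**2. The two forecasts.**

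| | Section 2.0 | Section 9.1 |
|---|---|---|
| Consented | 80 | 70 |
| Starters | 80 × 0.5 = 40 | not stated |
| Completers | 30 | 30 |
| Overall yield | 30/80 = 37.5% | 30/70 = 42.9% |

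The implied completion rate in Section 2.0 is 30/40 = 75%, taking the 30 as completers. At those rates, 70 consents give 70 × 0.5 × 0.75 = 26.25 completers. For 70 to be enough, either 40/70 = 57.1% must be eligible (with 75% completing) or 30/35 = 85.7% of starters must complete (with half eligible). The forecasts differ in assumed yield, not in their end point.

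**3. Does the consent total control anything?** Recruitment ends at 30 versus 30, with replacements until then. If 70 consents give 26 completers, the replacement rule keeps enrollment open. At the Section 2.0 rates, the number consented when the target is met is 30/(0.5 × 0.75) = 80, whichever total is printed.

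**4. What the 30 counts.** If every block counted, the starters needed at completion rate c would be 60/(1 + c). At c = 0.75 that is 34.3, so 40 starters would be more than needed. If completers are counted, the number is 30/0.75 = 40, which is the figure in Section 2.0. Section 9.1 separately gives 30 as the number completing the full study.

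**5. Power if a team counted blocks anyway.** Total variance is 900 + 900 = 1800 and the correlation is 0.5. With m completers and n starters per order, the variance of the within-order treatment difference is (1 − 0.5²) × 1800/m + (1 − 0.5)² × 1800/n = 1350/m + 450/n. Noncentrality is 2 × 28² divided by that variance.

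- 30 completers, no one-block participants (m = 15, n = 15): 1568/120 = 13.07, power 90.9%, agreeing with step 1.
- 30 completers plus 10 one-block (m = 15, n = 20): 1568/112.5 = 13.94, power 92.7%.
- 26 completers plus 8 one-block, which is 60 blocks (m = 13, n = 17): 1568/130.3 = 12.03, power 88.4%.

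**The case for a change.** The strongest opposing case is that a rule ending enrollment should not have to be inferred. Neither Section 5.0 nor Section 9.1 says whether a retained first block counts, and the replacement rule does not settle it, because a missed second block leaves an arm one short on either reading. The 75% completion rate also already presupposes that the 30 are completers. If blocks are counted, 40 starters reach 30 versus 30 with 20 completers and 20 one-block participants (40 + 20 = 60 blocks). Then m = 10, n = 20, and noncentrality is 1568/157.5 = 9.96. Power is about 81% by chi-square and about 77% to 80% in simulation, at or below the plan's target of at least 80%.

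The arithmetic stands, and so does the observation that no sentence defines the unit. The scenario does not. It needs half the starters to miss the second block, a rate no section states, and its 20 completers contradict the 30 expected in Section 9.1. It also departs from the power statement, which is for 30 participants and reproduces with both blocks.

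Nor does the 70 fit a block-counting reading. At the Section 2.0 rates, 35 starters would give 35 × 1.75 = 61 blocks, close to 60. But Section 9.1 itself ties the 70 to 30 completers, so that match is a coincidence of rates borrowed from another section.

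**Conclusion.** No change is needed. The difference between about 80 and 70 consents is a clerical inconsistency between two soft forecasts, 10 people apart, for the same 30 completers. Harmonizing them would not alter when enrollment stops, what is analyzed or what is concluded.

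The missing definition of the 30 is a gap that analysts would fill sensibly. The allowance of 40 starters, the expectation of 30 completers and the power for 30 participants all point to people with both blocks. On that reading power is 90.9%, or 92.7% once the first-block data of 10 non-completers are added. On the other reading, at 75% completion, it is about 88%.

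These figures rest on the plan's SDs and effect, on balanced dropout unrelated to outcome, and on a completion rate inferred from 40 starters and 30 completers rather than stated. Much lower completion combined with block counting would bring power to around 80%, but the plan's own expectation of 30 completers rules that combination out.

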3.0 DRUG PRODUCTS

Study drug: Lidocaine 1% PF vials will be purchased from Pfizer. API grade guanfacine will be purchased from Procos S.p.A., and Vanderbilt University Medical Center's Investigational Drug Service will compound and dispense a 10 ml sterile syringe with a sterile locking syringe cap containing 6 ml 1% lidocaine with 250 mcg guanfacine (see **Appendix A** for mixing instructions).

Active control: The active control drug (6 ml 1% lidocaine sterile injection) will be dispensed by VUMC's Investigational Drug Service and will be identical in appearance to the study drug.

Mode of administration: Trigeminal nerve block procedure

Trigeminal nerve block will occur with the patient supine in the procedure suite. Based upon landmark and fluoroscopic image, the needle insertion site will be located and infiltrated with 1ml of 1% lidocaine. A 22-gauge stimuplex needle will be advanced under fluoroscopic guidance to the pterygoid fossa. Active stimulation at 0.75 mV will be used to confirm needle tip approaching the V2 maxillary branch of the trigeminal nerve and reduced to 0.3mV upon patient sensation. After confirming that the needle tip is in position with no sensation felt by the patient at <0.3mV, and after negative aspiration for blood or cerebral spinal fluid (CSF), 0.25ml of iodinated contrast (Omnipaque 300) or gadolinium-based contrast agent (Omniscan) if allergic to iodinated contrast will be injected under digital subtraction fluoroscopy to ensure no vascular uptake. If vascular uptake occurs, the needle tip will be adjusted, and tested again for vascular uptake. After confirmation of the needle placement, 3ml of the study drug or active control will be delivered. The needle will be retracted and angled toward the V3 mandibular branch of the trigeminal nerve and confirmed in the same method with fluoroscopy and stimulation as above. After confirmation of needle placement, the remaining 3ml of the study drug or active control will be deposited. The needle will then be removed. The patient will be taken to the recovery room and monitored for 60 minutes.

4.0 ENROLLMENT AND INFORMED CONSENT

The study will be discussed with patients identified as potential candidates by primary criteria (above inclusion/exclusion listing) to determine suitability and willingness to participate in the study. Study staff will provide participants the opportunity to consent to participate. Study staff will inform participants that participation is voluntary, and if they enroll, they may withdraw from the study at any time, for any reason. Participants will be given ample opportunity to ask questions and will have their questions answered.

MyResearchAtVanderbilt (MRAV) is a participant repository recruitment tool available to Vanderbilt researchers that reaches over 18,000 My Health at Vanderbilt users that have previously confirmed they would like to be contacted directly for research. This repository provides investigators a forum for advertising to volunteers for a specific study. Email notifications are limited to IRB approved language, describe study specifics and provide contact information. To utilize this initiative, investigators complete a MRAV Access Request that is reviewed to ensure the recruitment tool and requested number of contacts are appropriate. To facilitate engagement and inform this pool of patients that they be contacted about study participation, the Study Coordinator will send an email approved by the IRB and MRAV study team.

Research Notifications Distribution List: Researchers can provide potential participants information about their study using the Research Notification Distribution List. This is a recruitment tool available to Vanderbilt researchers that reaches over 18,500 Vanderbilt faculty and staff, as well as some members of the Middle Tennessee community To facilitate engagement and inform this pool of patients that they be contacted about study participation, the Study Coordinator will send an email approved by the IRB.

The study will utilize EHR reports to identify and contact participants using VICTR's EHR Recruitment tool(s), including My Health at Vanderbilt mass Direct-to-Patient messaging and custom Reporting Workbench Report to identify potential participants.

Reporting Workbench (RWB) Reports are available/viewable in eStar. These reports are developed using real-time data and can be customized to meet study-specific inclusion/exclusion criteria. Research team members with eStar access and access to the Report Groups can view/run the reports as frequently as needed. While the report is generally limited to certain variables, it provides easy access to a patient's record for additional screening and confirmation of eligibility. A custom RWB report will be utilized to identify potential participants. The report will filter on study inclusion/exclusion criteria computable in the EHR and will display variables requested by the

study team. Additional variables used to filter the cohort include for mass messaging include: Research OK to Contact status, MHAV account activation/message status.

My Health at Vanderbilt (MHAV) Mass Direct-to-Patient messaging uses the MHAV patient portal to message a predefined cohort of patients who meet certain study-specific inclusion/exclusion criteria, have explicitly said OK to Contact for research, and have an active MHAV account. The IRB-approved MHAV mass messages are sent by the VICTR EHR Recruitment Support Team, not the study team. Potential participants who have an explicit OK to Contact documented in eStar will receive the following message based on the patient's MHAV notification preferences. If email and/or text notifications for research are not checked, the study information will simply appear on their research studies page in MHAV.

5.0 STUDY PROCEDURE

The study is a single center, randomized, double-blind, 2 x 2 crossover pilot study with two arms; study drug (guanfacine and lidocaine combination) and active control (lidocaine alone). Adult participants between 18 and 80 years of age who have been diagnosed with painful trigeminal neuropathy will be consented for the study. The study includes three visits; an initial visit for evaluation, consent, and baseline surveys followed by two procedural visits. After each procedural visit data will be collected for 14 days. Participants will be randomized in permuted pairs (to ensure balance after every second enrollment) to receive either study drug (guanfacine and lidocaine combination) or active control (lidocaine alone) for the first nerve block procedure. Following the first procedural visit and 14-day follow up period, the study team will assess inclusion and exclusion criteria and (if eligible) schedule the second procedural visit.

Assessment	Study Visit 1: Consent and screening (Day -15 to 0)	Study Visit 2: Procedure 1 (Day 1)	Follow-up period 1 (Day 2-14)	Study Visit 3: Procedure 2 (≥15 days after procedure 1)	Follow-up period 2 (14 days after procedure 2)
		Administrative P	rocedures		
Eligibility Review	X	X		X	
Informed Consent	X				
Demographics	X				
Pain History	X				
Baseline Pain	X	X	X	X	X
Medical History	X				
Concomitant Medications	X	X		X	
Surgical/ Past Treatments History	X				
Verbal Pregnancy Screen	X				
PROMIS Global 10- SF	X	X	X \$	X	X \$
Pain Interference	X	X		X	
Pain Intensity (VAS Score)	X	X #	X %	X #	X
Frequency of Attacks	X	X	X \$	X	X \$
Rescue Medications		X %	X %	X %	X
Randomization	X				
	Cl	inical Procedures/	Assessments		•
Physical Exam (general)	X	X		X	
Physical Exam (pain)	X				
Vitals (HR, RR, Temp, BP)	X	X		X	
Height/ Weight	X				
12-Lead ECG ^	X				
Continuous ECG monitoring		X		X	
Nerve Block Administration		X		X *	
Imaging MRI/ CT report +	X				
Adverse Events		X	X	X	X
		Laboratory Pro	cedures		
Urine Pregnancy Test		X		X	
Urine Drug Screen	X				

^{#:} Collected every 30 minutes for 8 hours by text message (REDCap) or patient diary

^{%:} Collected daily for up to 28 days by text message (REDCap) or patient diary

Collected weekly for up to 4 weeks by study nurse phone call

If pain score >5

^{+:} Review recent imagining, if not available then order as standard of care
^: Order 12-lead ECG as standard of care if one not available within 2 months of screening visit

Study Visit 1: Consent and Screening (Day -15 to Day 0)

Patients with facial pain will be evaluated in clinic; those deemed to have a diagnosis of painful trigeminal neuropathy will be considered for enrollment. Informed consent will be obtained prior to collecting data. Those patients that meet eligibility (inclusion/exclusion criteria outlined above) will be introduced to the study. Consented patients will become enrolled as study participants and will complete baseline measurement prior to randomization. Baseline data that will be collected includes demographics (name, age, sex), physical examination; heart rate and rhythm, blood pressure; comorbid health conditions and prior surgeries or treatments; current and past medications within 6 months. [name] will order an EKG if the participant has not had one within the past 2 months prior to the visit, as part of standard care. The targeted pain history will include pain duration, frequency of exacerbations, location, radiation, severity (VAS), quality, instigating event, exacerbations, alleviations, pain treatment frequency and duration of use (non-medical and medical treatments) and changes in pain over time. The targeted pain physical exam will include assessment of light touch test for allodynia and pinprick test for hyperalgesia of the trigeminal dermatome V1-3 regions of the face. Standard practice prior to trigeminal nerve block is to review recent MRI or CT imaging to ensure safety of needle approach to target location. If no recent imaging exists, this will be ordered as part of standard care prior to nerve block. Participants will be asked if there is a possibility they are pregnant. Women of childbearing potential will be educated on birth control methods and will agree to 2 methods of birth control that they will plan to use during the study period (abstinence is an appropriate method). A urine drug screen for illicit use of controlled substances will be obtained. Patient-reported outcome forms to be completed include the PROMIS Global-10 SF and Pain Interference forms. Current and average 24-hour pain (VAS) before procedure will also be recorded. Assessments will be recorded according to the patient's preference, either on paper or via electronic forms using REDCap. All data will be entered into REDCap.

Study Visit 2: Procedure 1 (Day 1)

Participants will be asked to record their pain intensity, 24- hour VAS and current VAS, before the procedure to establish a baseline pain score. Other data will be collected for secondary measures: frequency of pain attacks, basal and breakthrough opioid and non-opioid analgesic frequency and dose. Overall quality of life (PROMIS Global-10 short form) will be assessed.³⁹ Women of childbearing potential will undergo a urine pregnancy test prior to receiving the nerve block.

First trigeminal nerve block procedure: Participant will receive either study drug (guanfacine and lidocaine combination) or active control (lidocaine alone) for the trigeminal nerve block based on randomization. Participants will be monitored for pain intensity at 30-minute time intervals for the first 8 hours after block in addition to safety monitoring procedures. Participant responses will be collected at 30 minute intervals for the first 8 hours while in the recovery (first 60 minutes) and after discharge home, with responses allowed all the way until the next time point and actual time of the response being used in analysis. Assessments will be recorded according to the patient's preference, either on paper or via text message) using the Twilio application linked to REDCap. Patients will also receive a sheet with contact information for the study nurse.

First follow-up period (Day 2 to Day 14)

Participants will be monitored once daily at approximately the same timepoint for 14 days using text message generated using the Twilio application or recorded on a paper diary. Participants will also be monitored for any use of rescue medication (analgesics) once daily. The study nurse will monitor participants once weekly for overall quality of life via phone call using the PROMIS global 10 SF. Participants will be instructed to contact the study nurse with any adverse events directly by phone.

At the end of the first follow-up period, participants will be contacted for crossover to the other arm to receive the second trigeminal nerve block using the alternative drug (study drug or active control), not received during the first nerve block. At the second study visit, participants will record 24-hour VAS and current VAS, and the PROMIS Global-10 Short Form to establish baseline measurement again. Women of childbearing potential will undergo a urine pregnancy test prior to receiving the nerve block.

If VAS < 5 on the pain scale, participants will not be eligible for second trigeminal nerve block during the visit. Study nurse will continue monitoring the participant's pain intensity (daily through day 15, and weekly thereafter) to see if the participant pain is above 5 on the pain scale and eligible for the second block. In general, the study intends that participants would receive both treatments unless they experience intolerable toxicity. If a participant is unable or ineligible to receive second trigeminal nerve block, then the participant's data collected during the first nerve block will be included in the analysis. In addition, a replacement participant will be enrolled so that the minimum number of 30 for each arm is reached. An intention-to-treat analysis will be done post-hoc to evaluate any differential progress to second block between the initial randomized groups.

Second trigeminal nerve block procedure: Participant will receive second trigeminal nerve block followed by monitoring for pain intensity at 30-minute time intervals for the first 8 hours after block, again allowing responses all the way until the next time point.

Second follow-up period (14 days)

Participants will be monitored once daily at the same timepoint for 14 days using text message generated using the Twilio application or recorded on a paper diary. Participants will also be monitored for any use of rescue medication (analgesics) once daily. The study nurse will monitor participants once weekly for overall quality of life via phone call. Participants will be instructed to contact the study nurse with any adverse events directly by phone.

[figure not shown]

Figure: 1. Study Schema

